4.6.3 Classifications

Laboratory parameter values are abnormal low, if below the normal range, normal if within the normal range and abnormal high if above the normal range.

4.6.4 Notable Ranges

Notable ranges are defined for vital signs according to Table 3. Notable values are post-treatment values outside the notable ranges, whether above or below, and are indicated as *notably abnormal*.

Parameter	Notable Values and Changes from Baseline
Systolic blood pressure	90 mmHg or lower and decreased by 20 mmHg or more,
Systeme blood pressure	180 mmHg or greater and increased by 20 mmHg or more
Diastolic blood pressure	50 mmHg or lower and decreased by 15 mmHg or more,
Diastone blood pressure	110 mmHg or greater and increased by 15 mmHg or more
Pulse rate	50 bpm or lower and decreased by 15 bpm or more,
Puise fale	120 bpm or greater and increased by 15 bpm or more

Table 3: Definition of Notable Ranges of Vital Signs

4.7 Handling of Missing Data and Data Imputation

4.7.1 Partial Dates

If a date relevant for analysis is only partially available, it will be imputed by the central day of the time period of uncertainty, if this rule will be in line with potential dependencies of other complete dates in chronology. The time period of uncertainty is, for example, the calendar month, if the day is missing, or the calendar year, if day and month are missing. If the imputed date must be before or after a reference date, or between two reference dates, and the central day of the time period of uncertainty would not, the date will be imputed by the day of the time period of uncertainty closest to the central day but fulfilling the dependencies.

The approach of partial date imputation will be applied to visit dates, start and end dates of adverse events, start and end dates of concomitant medication, and the dates of last study drug application and of last contact, if partial.

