- d) Informed consent must be signed both by subject and investigator before any trial related procedures are carried out. For subjects requiring a washout period, informed consent must be completed prior to washout.
- e) For female subjects of childbearing potential. If there is a suspicion of pregnancy at any time during the trial, a urine sample will be obtained and tested.
- f) If a laboratory result is abnormal and judged as clinically significant, the investigator must follow-up as clinically appropriate (this may involve requesting repeat samples).
- g) AEs are to be collected from the date of signing the informed consent, i.e. also during the washout period.

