4.4.5 Treatment Emergency of Adverse Events

An AE is treatment-emergent if it occurs or deteriorates at or after the first application of the IP. Otherwise, an AE is not treatment-emergent.

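### A partial AE start date set to the middle of the unknown period can place an on-treatment AE before the first application and out of the treatment-emergent tables

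*SAP*

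**What the plan says.** **Dating.** Under SAP 4.7.1 a partial date becomes the middle of the unknown period: "it will be imputed by the central day of the time period of uncertainty", provided that this agrees with the order of other complete dates. The unknown period is "the calendar month, if the day is missing, or the calendar year, if day and month are missing". Where the date has to fall before, after or between reference dates and the central day does not, "the date will be imputed by the day of the time period of uncertainty closest to the central day but fulfilling the dependencies". The section does not list which reference dates bind which variable. Its scope is explicit: the approach "will be applied to visit dates, start and end dates of adverse events", among others.

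**Classification.** SAP 4.4.5: "An AE is treatment-emergent if it occurs or deteriorates at or after the first application of the IP". Every other AE is not treatment-emergent. Nothing there, in 4.7.1 or in 5.6 says how to class an AE whose partial start date could fall on either side of the first application.

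**Collection.** Protocol Table 7-1, footnote g: "AEs are to be collected from the date of signing the informed consent, i.e. also during the washout period". Screening may last up to 30 days. If no washout is needed, screening and Visit 1 may be on the same day.

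**Reporting.** SAP 5.5.4 and Tables 14.3.1.2 to 14.3.1.9 present treatment-emergent AEs only. Table 14.3.1.1 (overview) and the AE listings carry no such limit in their titles.

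**The concern.** The two rules work in sequence. 4.7.1 turns an unknown onset into a definite date, and 4.4.5 reads that date as if it had been observed. When the first application falls after the central day of the onset month, the imputed start precedes dosing even though the AE may have begun afterwards.

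The usual safeguard in a safety analysis is to count an AE as treatment-emergent unless the available date information shows that it was not. The plan has no such rule. Safety is the trial's secondary objective, and Protocol 8.7 rests the safety assessment mainly on AE frequency, so the treatment-emergent flag decides what appears in the main AE tables. The events exposed are those starting soon after the first dose.

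**Working it through.** The plan states no figure here, so there is none to reproduce. The check is a worked example, a count over the calendar, and the year-only case.

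**Example (illustrative dates).** Consent is 1 March, first application 20 March, and AE start is recorded only as March. The central day of a 31-day month is the 16th. 16 March is after consent, so the chronology clause does not act. 16 March is before 20 March, so the AE is not treatment-emergent, although onset on 20-31 March fits the record.

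**Assumptions for the count.** First-dose dates are uniform over a 365-day year, onset is uniform over the window, the day is missing independently of timing, and consent is before Day 0.

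**Formula.** Take a month of n days with central day c. Misdating needs a first-dose day d > c and an onset on days d to n of that month. With m = n - c:
- misdated pairs per month = m(m + 1)/2
- all on-treatment pairs in the first-dose month = n(n + 1)/2

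An even-length month has two possible central days, and the SAP does not choose between them.

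| Month length | Months | n(n+1)/2 | Misdated, earlier c | Misdated, later c |
|---|---|---|---|---|
| 31 | 7 | 496 | 120 (c = 16) | 120 (c = 16) |
| 30 | 4 | 465 | 120 (c = 15) | 105 (c = 16) |
| 28 | 1 | 406 | 105 (c = 14) | 91 (c = 15) |
| Year | 12 | 5,738 | 1,425 | 1,351 |

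**Results, as shares of on-treatment onsets with the day missing**
- In the first-dose month: 1,351/5,738 = 23.5% to 1,425/5,738 = 24.8%.
- Days 0-56 (365 × 57 = 20,805 pairs): 6.5% to 6.8%.
- Days 0-70 (365 × 71 = 25,915 pairs): 5.2% to 5.5%.
- Days 0-14 (365 × 15 = 5,475 pairs): 24.7% to 26.0%.

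**Consent as a lower bound.** With consent 7, 14 or 30 days before Day 0, these shares do not change. With consent on Day 0, the bound moves the imputed date to Day 0 and the share is 0%.

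**Year only.** The Protocol synopsis puts trial initiation in Q4 2018. The central day of 2018 is 2 July. A year-only 2018 onset in a subject first dosed in that quarter is therefore dated 2 July, or the consent date if that bound is applied. Both precede the first application unless consent was on Day 0.

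**The other direction.** With the earlier central day and before any end-date constraint, day-missing onsets that truly preceded dosing are dated on or after Day 0 in 966/2,555 = 37.8% (onset in the 7 days before), 1,344/5,110 = 26.3% (14 days) and 1,351/10,950 = 12.3% (30 days).

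**From partial dates to all AEs.** The documents give no rate of partial dates. If 1% to 10% of on-treatment AEs lacked the start day (an assumption), the share of those AEs misdated would be 0.01 × 5.2% = 0.05% to 0.10 × 6.8% = 0.68%.

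**The case against.** The strongest reply is that this will rarely matter. AEs are sought at every visit, including Week 1 and the Week 2 call, and eCRF errors are queried. A site should seldom lose the day of a recent onset, and a year-only date is less likely still. This stands, and it limits the size of the problem. It does not make the rule correct for the dates it was written to handle.

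Other parts of the reply also stand:
- Same-day consent and Visit 1 removes the problem. A reader might infer that everyone dosed in the second half of a month is affected. The documents do not support that.
- The deterioration limb of 4.4.5 can retain some events, so date of onset is not the only route to treatment emergence.
- A reader might infer that affected AEs disappear from the safety report. They do not: the listings and, by its title, Table 14.3.1.1 still hold them. Local skin reactions are graded at each on-site visit from Visit 1 and tabulated without using AE onset dates.
- A reader might infer a bias in favour of MC2-01 cream. The rule is the same in all arms, errors run both ways, and no difference between arms is shown.

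One part does not stand, namely that the chronology clause already covers this. It acts only where a date has to respect a reference date. The first application is not named as one, and it cannot be a natural bound when AEs are collected during washout.

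**Conclusion.** The concern holds in a limited form. Followed as written, SAP 4.7.1 and 4.4.5 can class an on-treatment AE with a partial start date as not treatment-emergent and omit it from Tables 14.3.1.2 to 14.3.1.9. The conditions are consent before Day 0, first application after the central day, and no later deterioration.

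The shares are about 5-7% of day-missing on-treatment onsets overall, about 24% in the first-dose month and about 25-26% on Days 0 to 14. They rest on evenly spread first-dose and onset dates, and they are shares of partial dates, not of all AEs. The documents do not show that any AE has been or will be lost, and the absolute number is probably small. Because the stated rule can give a wrong class and the repair is cheap, it should be changed before unblinding.

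A related ambiguity should be settled at the same time. SAP 4.7.2 rules out imputation of missing data for safety-set analyses, while 4.7.1 imputes the AE dates on which the safety-set tables depend.

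**What to change.** Add to SAP 4.4.5 and 4.7.1:

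> If a partial AE start date does not exclude onset on or after the first IP application, and the AE end date is not before that application, the AE is treatment-emergent. Its start is imputed as the later of the first-application date and the first day of the unknown period.

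Apply the end-date condition to the end date as recorded. If start and end are both known only as March in the example, central-day imputation would put the end on 16 March too, and the new rule would fail.

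Keep the central-day rule for other dates. State in 4.7.2 that its no-imputation sentence for the safety set does not cover partial dates.

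**Effect.** No true on-treatment onset with a partial start date would be classed as pre-dose.

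**Cost.** A short SAP addition and one programming condition. Some pre-treatment AEs will be counted as treatment-emergent. Before the end-date condition, these are all day-missing pre-dose onsets in the first-dose month. For onsets in the 30 days before dosing that is 5,373/10,950 = 49% (the sum of n(n - 1)/2 over the 12 months, divided by 365 × 30), against 12.3% under the present rule with the earlier central day. The end-date condition lowers this, the number should be few because partial dates should be few, and the rule is the same in all arms.

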4.7.2 Missing and Invalid Data

Data is missing if unavailable. Data is invalid if not considered for analysis. Invalidity of data is defined below, where applicable. On some analyses as indicated below, missing or invalid data will be replaced by the last observation carried forward (LOCF), by non-responder imputation (NRI) or by multiple imputation (MI).

Single Imputation by LOCF

On LOCF, a missing value is imputed by the last available value carried forward to the visit with the value missing until and including the last visit.

Single Imputation by NRI

On NRI, a missing value is imputed by a value representing non-response. Non-response is defined per endpoint below.

Multiple Imputation

Post-baseline missing or invalid data will be multiply imputed within treatment groups in two steps [10]. At first, any potential intermediate missing data will be imputed 100 times using a Markov Chain Monte Carlo (MCMC) method to obtain a monotone missing data pattern. In a second step, imputation is done using a monotone regression method, fitting an analysis of covariance (ANCOVA) model stepwise visit by visit. The ANCOVA model adjusts for the effects of analysis sites and baseline PGA as factors and the baseline value of the respective endpoint as a covariate. For each treatment group and each copy of the dataset, the estimated parameters and their variances are used to impute the endpoint. Starting with Week 1, the procedure is repeated on Week 4, Week 6 and Week 8, adding the possibly imputed values of the previous visits as covariates. On MI, missing score data is handled like missing continuous data.

If MI is applied to a dichotomized endpoint, the procedure is followed before dichotomization.

For analyses on the PPS or the safety set, no imputations will be made for missing data. For analyses on the FAS, LOCF, NRI and MI will be made for missing and invalid data.

5 Statistical Methods

5.1 Conventions for Inference

The two-sided level of significance is set to $\alpha = 0.05$, the one-sided level of significance to $\alpha = 0.025$.

5.2 Statistical Hypotheses

Let μ_M , μ_V and μ_C be estimators of treatment effect per endpoint for MC2-01 cream, MC2-01 cream vehicle and active comparator, respectively. The following four statistical hypotheses will be tested.

- a. H_{0a} : $\mu_M = \mu_V$ versus H_{1a} : $\mu_M \neq \mu_V$,
- b. H_{0b} : $\mu_C = \mu_V$ versus H_{1b} : $\mu_C \neq \mu_V$,
- c. H_{0c} : $\mu_M \mu_C \le -\Delta$ versus H_{1c} : $\mu_M \mu_C > -\Delta$,
- d. H_{0d} : $\mu_M = \mu_C$ versus H_{1d} : $\mu_M \neq \mu_C$.

where Δ is a non-inferiority margin. In two-sided H_{0a}, H_{0b} and H_{0d}, if the hypothesis is rejected, superiority of the group with greater estimate is concluded. On one-sided H_{0c}, if the lower limit of the two-sided 95% confidence interval of the estimate of the treatment difference is greater than - Δ , non-inferiority of MC2-01 cream as compared to active comparator is concluded.

The non-inferiority margin Δ is 12 percentage points on the primary endpoint mPASI and 10 percentage points on the first secondary endpoint PGA success.

5.3 Overall Strategy and Issues of Multiplicity

The statistical hypotheses on the primary and secondary endpoints will be tested confirmatorily in a hierarchical approach. The hierarchical approach ensures that the familywise type 1 error is controlled. According to the definitions in Section 5.2, hypotheses will be hierarchically tested starting with H_{0a} and H_{0b} . If, and only if H_{0a} and H_{0b} are, H_{0c} is tested confirmatorily. Hierarchical testing, H_{0a} to H_{0c} , will be done on the primary endpoint, mPASI, at first. If, and only if, non-inferiority of MC2-01 cream versus active comparator is claimed on the primary endpoint, the hierarchical testing procedure is continued on the first secondary endpoint, PGA success on the body. If, and only if, non-inferiority of MC2-01 cream versus active comparator is claimed on the first secondary endpoint, H_{0d} is tested on the second secondary endpoint, mPASI 75, where also H_{0a} is tested, and the fourth secondary endpoint, PGA success on the scalp, if, and only if, leading to rejections on the previous steps. In case hypotheses cannot be rejected, testing on this and all preceding hypotheses is exploratory only. The strategy is summarized in the following display.

Table 4: Overview on Hierarchical Hypothesis Testing Strategy with Different Endpoints and Hypotheses

Endpoint	Step	Hypothesis
%change in mPASI at Week 8	1	H _{0a} for superiority of MC2-01 cream over vehicle
	2	H _{0b} for superiority of active comparator cream over vehicle
	3	H _{0c} for non-inferiority of MC2-01 cream and active comparator
PGA success on the body at Week 8	4	H _{0a} for superiority of MC2-01 cream over vehicle
	5	H _{0b} for superiority of active comparator cream over vehicle
	6	H _{0c} for non-inferiority of MC2-01 cream and active comparator
PTCS at Week 8	7	H _{0d} for superiority of MC2-01 cream over active comparator
%change in mPASI at Week 8	8	H _{0d} for superiority of MC2-01 cream over active comparator
PGA success on the body at Week 8	9	H _{0d} for superiority of MC2-01 cream over active comparator
mPASI 75 at Week 8	10	H _{0a} for superiority of MC2-01 cream over vehicle
	11	H _{0d} for superiority of MC2-01 cream over active comparator
PGA success on the scalp at Week 8	12	H _{0a} for superiority of MC2-01 cream over vehicle
-	13	H _{0d} for superiority of MC2-01 cream over active comparator

For definitions of hypotheses, see Section 5.2

Efficacy endpoints will be analyzed by different estimands, following a treatment-policy strategy (primary estimand) and a hypothetical strategy (secondary estimand). Only on PTCS, a while-on-treatment strategy will be followed.

According to the *treatment-policy strategy*, all available data will be used, regardless of treatment and treatment adherence. Missing data will be imputed.

According to the *hypothetical strategy*, only data will be used under the IP and while adhering to the IP. If any other psoriasis treatment is used, i.e. treatment that according to medical judgement may improve psoriasis, data during and after the period of other psoriasis treatment intake is invalid and will not be used. Furthermore, data will not be used of periods of potential non-adherence to the IP. Non-adherence will be given if the IP is applied on less than 70% of the days from Day 0 to Week 4, Week 4 to Week 6, and Week 6 to Week 8, respectively. Non-adherence to the IP is derived from days with treatment non-compliance. Missing and invalid data will be imputed.

According to the *while-on-treatment strategy*, all available data will be used with treatment within 7 days before assessment. Data without treatment within 7 days before assessment is invalid and will not be used.

Hierarchical testing applies to the primary analyses per endpoint, not to any sensitivity analyses as described below.

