8.6.1.1 Analysis of primary endpoint

Superiority analysis

First the percentage change in mPASI from baseline to Week 8 for MC2-01 cream and the active comparator will be compared with that of MC2-01 cream vehicle for a superiority evaluation using the treatment-policy estimand for the ITT population and imputing missing data using MI.

The comparison will be done using an ANCOVA model including treatment, site, and baseline PGA as factors, and baseline mPASI as covariate. The estimated differences between MC2-01 cream and MC2-01 cream vehicle, and between active comparator and MC2-01 cream vehicle, will be reported together with the associated standard error, the 95% confidence interval, and a test corresponding to no difference between treatments.

Non-inferiority analysis

Next, if and only if superiority to MC2-01 cream vehicle can be claimed for both MC2-01 cream and active comparator on the 5% significance level, MC2-01 cream will be compared to active comparator for a non-inferiority evaluation using the treatment-regimen estimand for the ITT population and imputing missing data using MI.

Percentage change in mPASI from baseline to Week 8 will be compared between MC2-01 cream and active comparator for a non-inferiority evaluation using the -12 percentage points non-inferiority margin. The comparison will be done using the same model as applied for the analysis of superiority vs. vehicle as described above: an ANCOVA model including treatment, site, and baseline PGA as factors, and baseline mPASI as covariate. The estimated difference between MC2-01 cream and active comparator will be reported together with the associated standard error, and the 95% confidence interval. If the lower limit of the 95% confidence interval is above -12 percentage points, non-inferiority is demonstrated.

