8.6.2 Secondary Efficacy Endpoints

The secondary efficacy endpoints are:

- PGA success on the body (trunk and/or limbs) at Week 8
- Subject assessment of treatment convenience at Week 8 using the PTCS Analysis of secondary endpoints

To control the global Type-I error, the secondary endpoints will be tested in hierarchical order, if and only if non-inferiority can be demonstrated for the primary endpoint. The endpoints will be analyzed using the treatment-regimen policy estimand for the ITT population.

For PGA success, missing PGA values will be imputed using MI considering PGA as a continuous endpoint.

• PGA success: PGA success of both MC2-01 cream and active comparator will be compared with that of MC2-01 vehicle for a superiority evaluation. The comparison will be done using a logistic model with treatment, baseline PGA, and site as factors.

Clinical Trial Protocol

MC2-01-C7

16 October 2018 Version 2.0

- PGA success: Non-inferiority of MC2-01 cream versus active comparator. PGA success will be compared between MC2-01 cream and active comparator for a non-inferiority evaluation using a -10 percentage points non-inferiority margin, as -10 percentage point is considered the largest clinically acceptable loss of effect. This non-inferiority margin was also used in the MC2-01-C2 trial (1). The percentage of subjects in each group with treatment success will be calculated along with its 95% confidence interval (CI) using normal approximation. A 95%, 2-sided CI for PM-PA, where PM and PA are the PGA treatment success rate at Week 8 for MC2-01 cream and active comparator respectively, will be computed using normal approximation using Proc FREQ with RISKDIFF option. MC2-01 will be considered non-inferior to active comparator if the lower bound of the 2-sided 95% CI is ≥ -10% points.
- PCTS: Superiority of MC2-01 cream versus active comparator. A PCTS score is considered invalid, if subject has discontinued study medication more than 7 days prior to the day of assessment. Missing and invalid PTCS scores will be imputed using the last valid measure prior to the visit (LOCF). This approach corresponds to a "PCTS while on treatment" estimand. The PCTS score will be compared between MC2-01 cream and active comparator using an ANCOVA model with treatment, baseline PGA, and site as factors.

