5.5.2 Secondary Efficacy Endpoints

If the primary analysis of the primary endpoint yields rejection of all hypotheses, hierarchical testing is continued on secondary efficacy endpoints, with PGA success at first, followed by PTCS.

PGA Success

The first and fourth secondary efficacy endpoints are the percentage of subjects with PGA success on the body and on the scalp at Week 8, respectively, as defined in Section 2.4.1.

Primary Analysis

Considering PGA as a continuous endpoint, missing data will be imputed using MI as described in Section 4.7.2. On derived PGA success following the treatment-policy strategy, hypotheses will be tested, and comparisons of treatment groups done using a model of logistic regression as described in Sections 5.2 and 5.4.1.

Sensitivity Analyses

Two sensitivity analyses are planned on the first secondary endpoint, an analysis following the treatmentpolicy strategy on the FAS using NRI, and an analysis following the hypothetical strategy on the FAS using MI. On PGA success, non-response is defined as no PGA success.

In a first sensitivity analysis, missing data will be imputed using NRI as described in Section 4.7.2. On PGA success following a treatment-policy strategy, hypotheses will be tested, and comparisons of treatment groups done using a model of logistic regression as described in Sections 5.2 and 5.4.1.

In a second sensitivity analysis, missing and unused data will be imputed using MI as described in Section 4.7.2. On PGA success following a hypothetical strategy, hypotheses will be tested, and comparisons of treatment groups done using a model of logistic regression as described in Sections 5.2 and 5.4.1.

PTCS

The second secondary efficacy endpoint is the PTCS total score at Week 8. The PTCS total score will be analysed by means of an analysis of variance with treatment, analysis site and baseline PGA as factors.

Analysis of PTCS is following a while-on-treatment strategy using data as described in Section 5.3. Missing and invalid data will be imputed using LOCF as described in Section 4.7.2.

Primary Analysis

The primary analysis of PTCS will be based on the FAS following the while-on-treatment approach using LOCF to impute missing and invalid data.

Sensitivity Analyses

A sensitivity analysis of PTCS will be based on the PPS following the while-on-treatment approach using LOCF to impute missing and invalid data.

mPASI 75

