5.6 Changes and Clarifications to Analyses Planned in the Study Protocol

Analyses are planned according to protocol. Defined as other endpoints in the protocol, mPASI75 at Week 8 and PGA of psoriasis severity on the scalp at Week 8 are promoted to secondary endpoints at the end of the hierarchical testing strategy on secondary endpoints. For PGA on the scalp, the same definition of PGA success as on the body will be applied, on a subpopulation of subjects with psoriasis on the scalp at baseline. To clarify, BSA assessment is listed under other endpoints. Notable laboratory normal ranges will not be defined.

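### SAP 5.3 states the consequence of a failed step backwards: it downgrades the earlier hypotheses instead of the later ones

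*SAP*

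**What the plan says.** SAP section 5.3 describes a hierarchical procedure, and Table 4 lists it as steps 1 to 13. Steps 1 to 3 concern percentage change in mPASI: each active treatment against vehicle, then non-inferiority of MC2-01 cream to the active comparator. Steps 4 to 6 repeat this for PGA success on the body. Steps 7 to 13 cover superiority on PTCS, mPASI, PGA success, mPASI 75 and PGA success on the scalp.

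The paragraph ends with the rule for a failed step: "In case hypotheses cannot be rejected, testing on this and all preceding hypotheses is exploratory only".

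The other statements on order run forwards:

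- SAP 5.3 moves to PGA success under this condition: "If, and only if, non-inferiority of MC2-01 cream versus active comparator is claimed on the primary endpoint". For the later endpoints it requires testing to proceed "if, and only if, leading to rejections on the previous steps".
- SAP 5.5.2: "If the primary analysis of the primary endpoint yields rejection of all hypotheses, hierarchical testing is continued on secondary efficacy endpoints".
- Protocol 8.6.2: "the secondary endpoints will be tested in hierarchical order, if and only if non-inferiority can be demonstrated for the primary endpoint".

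The primary non-inferiority conclusion itself carries no condition on later tests. Protocol 8.6.1.1 says: "If the lower limit of the 95% confidence interval is above -12 percentage points, non-inferiority is demonstrated". SAP 5.2 likewise says that, once the confidence limit clears the margin, "non-inferiority of MC2-01 cream as compared to active comparator is concluded".

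**The concern.** A fixed-sequence procedure spends the full significance level at each step and stops at the first failure. What is lost at a failure is the right to make confirmatory claims from that step onwards. Nothing rejected earlier is affected, because each earlier test depended only on those before it.

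The SAP sentence reverses this. With the steps numbered in testing order, *preceding* can only mean lower-numbered steps. A miss at step 13, superiority over the comparator on scalp PGA success, would turn the primary non-inferiority result at step 3 into an exploratory one. The sentence also omits what a reader needs from it, namely the status of the steps after the failure.

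At stake is the label on the trial's main claim. The SAP is the pre-specified record of what counts as confirmatory. If the wording is corrected only after the data are seen, the correction can be challenged as driven by the results.

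**Working it through.** **Direction of the rule**

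| Place | What depends on what |
|---|---|
| SAP 5.3, step 3 to step 4 | step 4 depends on non-inferiority at step 3 |
| SAP 5.3, steps after 7 | later tests depend on rejections at the steps before them |
| SAP 5.5.2 | secondary tests depend on primary rejections |
| Protocol 8.6.2 | secondary tests depend on primary non-inferiority |
| SAP 5.3, failed-step sentence | status of lower-numbered steps depends on a later test |

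Only the last row runs backwards. The step 3 claim must already have been made before step 4 is looked at, so it cannot also wait for the outcome of steps 4 to 13. SAP 5.6 opens with "Analyses are planned according to protocol" and then lists its changes; a backward rule is not among them, so it cannot be read as a deliberate departure.

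**What literal use would do to the primary claim**

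Inputs: SD 38, 204 subjects per active arm, true difference 0, two-sided 5% level, stated power 88.9% (Protocol 8.2); margin 12 percentage points (SAP 5.2). Differences are oriented here so that positive favours MC2-01 cream.

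1. Standard error of the contrast between the active arms: 38 × √(2/204) = 3.763.
2. The plan's own figure. Power of step 3 at zero difference: Φ(12/3.763 − 1.96) = 0.891. The noncentral t with 406 degrees of freedom gives 0.889. The stated 88.9% is reproduced.
3. Step 3 passes when the observed difference exceeds −12 + 1.96 × 3.763 = −4.63 (with t: −4.60).
4. Step 8 is superiority on the same contrast. It favours MC2-01 cream when the observed difference exceeds 1.96 × 3.763 = +7.37 (with t: +7.40). At zero difference this has probability 0.025.
5. Any result that passes step 8 in favour of MC2-01 cream also passes step 3, so the probability of passing both is 0.025. A simulation with 2,000,000 draws gave 0.891 for step 3 and 0.0249 for both.
6. Counting a step 8 rejection in the comparator's favour does not help. It needs an observed difference below −7.37, so the lower confidence limit is below −7.37 − 7.37 ≈ −14.75 and step 3 has already failed.
7. The remaining steps must also pass, which can only lower the figure. Hence 2.5% is a ceiling.

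The ceiling depends on the true difference. If MC2-01 cream were truly better by 7.37 points, step 8 would pass with probability Φ(7.37/3.763 − 1.96) = 0.50. Step 3 would then have power Φ((12 + 7.37)/3.763 − 1.96) = Φ(3.19), above 99%. Literal use would still remove confirmatory status in at least half of trials.

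**Familywise error**

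As long as the forward conditions are followed, the literal sentence only takes claims away. It adds none, so the familywise error is not inflated.

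**The case against.** The strongest reply is that this is one wrong word and that the plan already shows what was meant. SAP 2.4.1 says primary and secondary endpoints are evaluated confirmatorily through the hierarchy, SAP section 1 commits to analysis in line with the protocol, and the protocol's ordering is purely forward. No estimate, interval or p-value changes, only a label, and only if someone follows a reading that nobody is likely to have intended. Setting 2.5% beside 88.9% could then make a wording error look like a loss of power. It can also be said that Protocol 8.6.1.1 and SAP 5.2 state when non-inferiority is shown without assigning confirmatory or exploratory status, so the direct conflict lies inside SAP 5.3. Finally, nearby sentences in that paragraph appear incomplete in the text available, so something close by may have been lost.

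Much of this stands. The intended rule is recoverable, the error rate is safe, and the 2.5% describes literal use, not the trial's power. The sharpest contradiction is within SAP 5.3, with the other passages as support. The failed-step sentence itself, however, is complete, and nothing in either document corrects it. That the meaning can be inferred is a reason to rate the point as moderate; it does not justify leaving the text as it is.

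**Conclusion.** The sentence is wrong as written and should be corrected. It is most likely a drafting error. It does not threaten type I error control, the test order or any analysis. It does leave the SAP with two incompatible answers on whether a met primary non-inferiority result stays confirmatory when a later test fails.

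Under the plan's assumptions (SD 38, 204 per active arm, zero true difference), literal use would keep the primary claim confirmatory in at most 2.5% of trials instead of the planned 88.9%. That ceiling would be higher if MC2-01 cream were truly better than the comparator. With the corrected wording, no later failure touches step 3.

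**What to change.** Before unblinding, amend the failed-step sentence in SAP 5.3. Replace *preceding* with *subsequent*, tie it to the step order in Table 4, and add a clause that rejections at earlier steps remain confirmatory. A workable form: if a step in Table 4 does not lead to rejection, that step and every later step are exploratory, while rejections at earlier steps keep their confirmatory status.

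The cost is one word and one clause in the SAP. Test order, significance level, sample size, analyses and the protocol are unaffected.
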